6.3 MEASURES TO MINIMIZE BIAS: RANDOMIZATION AND BLINDING

Clinics covered by the same care provider who will deliver SPIRIT sessions will be combined to one cluster to avoid risk of contamination; this results in clusters (4 in GA, 3 in NC, 8 in NM, 5 in PA and 8 in VA). Because the numbers of available patients substantially vary across the clusters, to minimize group imbalance clusters will be stratified to three sizes: small (patient census ≤ 52), medium (53-105), and large (≥ 106). We will randomize clusters to either SPIRIT or usual care plus delayed SPIRIT, with randomly permuted blocks (sizes of 2 and 4) within cluster size stratum nested in each state, using a pseudo-random-number generator, by the Study Coordination Center.

Before the study starts, the Study Coordination Center will inform the group assignment for each cluster to the site PIs, with a unique ID consisting of abbreviations for state and cluster size stratum. While the heterogeneity in minority race/ethnicity across clusters improves the study's generalizability, stratification or pairing clusters by race/ethnicity is not feasible because some clinics uniquely serve one race with no comparable clinics within state. Group imbalances on race/ethnicity and other potential confounding factors will be examined and adjusted for in the analyses. The cluster randomized design prevents blinding patient-surrogate dyads and dialysis care providers to group allocation. However, research staff assessing effectiveness outcomes will be blind to group assignment.

For Supplement Aims:

[name] (biostatistician/Co-I) will generate a randomization scheme using stratified (by race), permuted block randomization with block size 5, using a random-number generator. Dyads will be randomized with equal allocation (1:1) to SPIRIT or usual care. Due to the nature of the intervention, blinding dyads to their group allocation is impossible, but the research staff assessing outcomes will be blind. Immediately after the completion of the baseline assessment by phone, the data collector will open a sealed envelope to identify group assignment and schedule an intervention session to take place ~ 2 weeks hence for SPIRIT as well as a follow-up data collection session in the next 2-3 days.

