- **The preparedness outcomes measures** will be assessed at baseline and 2-3 days after the intervention.
- **Surrogates' post-bereavement psychological distress** will be assessed using the HADS, which will be completed at baseline and 1 month post patient death.
- **Patients' level of articulation of end-of-life wishes:** Using a "quantitizing" technique of qualitative data analysis,³⁹ two raters will independently review SPIRIT session transcripts focusing on the values of

treatment outcomes and the goals of care discussions and rate the level of patient's articulation of end-of-life care preferences on a 3-point scale (3=expressed wishes very coherently, 2=somewhat coherently, 1=unable to express wishes coherently). Inter-rater reliability (percent agreement) will be established, targeting $\geq 90\%$.

- **Care decisions (assessed at 6 months post intervention or after the patient's death, whichever occurs first):** Stopping dialysis, DNR order, and hospice enrollment are major care decisions that must involve the treating physician (or APRN) and social worker. These decisions are also required to be documented in the CMS Form 2746 in the event of a dialysis patient's death. On a monthly basis, the research coordinator will check in with the outpatient dialysis APRN to track these care decisions and will be aggregated at 6 months.
- **Descriptors and Potential Covariates (collected at baseline):** Patients and surrogates will each complete a Sociodemographic Profile which includes demographic information and previous end-of-life decision-making experience. Patients' clinical characteristics (e.g., date of dementia diagnosis, etiology of dementia, and comorbid conditions) will be abstracted from the patient's medical records.

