9.2 SAMPLE SIZE DETERMINATION

We have an adequate sample size to detect clinically meaningful differences between SPIRIT and usual care for our primary outcomes. Statistical power is based on a random effects models: a generalized linear mixed model for binary outcomes (e.g., dyad congruence) and a linear mixed model for continuous outcomes (e.g., patient decisional conflict).

We conducted a simulation study to estimate power with 2-sided significance level alpha=.05, corrected for anticipated dropout and potential intraclass correlations (ICCs) ranging .01-.04, based on ICCs observed in our prior work. To estimate the power more conservatively, we used the effect sizes observed at 2 months²⁰ rather than those at 2 weeks,¹⁸ which are larger (e.g., for the composite outcome, *OR*=1.8 at 2 months, *OR*=4.4 at 2 weeks). The overall power to detect clinically meaningful differences is excellent for the primary outcomes and good for the post-death outcomes.

Power for comparing SPIRIT and usual care with 19 clusters				
Aim 1	Percent or min. difference	OR or variance	ICC ^a	Estimated power
Dyad congruence	48%	OR =2.0	0.02 0.04	0.92 0.84
Patient DCS	d =0.24	0.23	0.01 0.10	0.98 0.81
Surrogate DMC	d =0.22	0.20	0.01 0.10	0.99 0.80
Composite outcome	47%	OR =2.0	0.02	0.93
Aim 3				
Anxiety	d =1.35	7.0	0.01 0.03	0.84 0.80
Depression	d =1.60	10.0	0.01 0.03	0.85 0.79
PTSS-10	d =4.75	90.0	0.01 0.03	0.85 0.78

^a observed ICCs in our prior work; *d*=1/2 *SD*.

DCS, decisional conflict scale; DMC, decision-making confidence.

For Supplement Aims:

Because this is a pilot study, prior estimates of effect sizes were not available; thus a traditional sample size calculation was not performed. Instead we focused on calculating the minimum effect size that can be detected with adequate power (>=80%). Based on preliminary calculations, we found that a sample size of 30 will achieve 80% power to detect an effect size (Cohen's *f*²) of 0.28 (moderate-high), attributable to the treatment group indicator using an F-test at a 5% significance level. We will use the estimates of effect sizes obtained from this study for sample size calculations in future larger studies.

Supplement cohort study:

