9.4.2 ANALYSIS OF THE PRIMARY ENDPOINT(S)

SPIRIT effectiveness on the preparedness outcomes: Dyad congruence and the composite outcome (binary variables) will be analyzed by fitting a generalized mixed effects model for each, where the binary outcome is modeled in terms of a logit link⁹⁰ with both a random intercept and random slope to control for variation within and between subjects and clusters. The model also includes the intervention SPIRIT, cluster size and their interaction. For patient DCS and surrogate DMC scores, we will replace the logit link by the identity link with an additional error term. These models will allow us to examine whether SPIRIT was superior to usual care in the primary outcomes at 2 weeks and whether the effect of SPIRIT varies by cluster size. The analysis will be adjusted for potential covariates, such as race/ethnicity, and rural-urban status, in the model, including interaction between treatment and race/ethnicity.

For Supplement Aims:

To account for small sample size, resampling methods will be used for all analyses and 95% bootstrap confidence intervals of the differences in outcome scores will be reported.

- 1) Aim 1. SPIRIT effects on the preparedness outcomes:** For testing the effect of the intervention on dyad congruence, a paired binary outcome (congruent or not congruent), McNemar's test will be used. In addition, a logistic regression model will be used to test for differences in post-intervention outcomes by groups after adjusting for potential covariates. The adjusted ratio of odds of congruence in the intervention group versus the control group will be evaluated and reported as an effect size estimate.
- 2) Aim 1. SPIRIT effects on care decisions:** Differences in proportion of decisions made (e.g. stopping dialysis, DNR order, and hospice enrollment etc.) at 6-month follow up or death of patient will be described across groups and used as effect size. We will also explore time to event analysis to assess the difference in rate of risks between the two groups using non-parametric and semiparametric methods.
- 3) Aim 2. Surrogate post-bereavement distress (HADS scores):** Differences in the HADS subscale scores between the intervention and control groups will be assed using t-tests. Because, we estimate a 50% rate of death during the study, the number for this analysis would be n=15. A standardized difference between groups will be used as an effect size estimate.

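### Dementia pilot: an ordinary adjusted logistic regression in 30 dyads, with an open covariate list, exaggerates a non-null congruence odds ratio and may give no finite estimate

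*Combined protocol and SAP*

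**What the plan says.** Section 9.4.2 (For Supplement Aims, Aim 1) plans McNemar's test for dyad congruence and, in addition, a model: "a logistic regression model will be used to test for differences in post-intervention outcomes by groups after adjusting for potential covariates". The adjusted OR for SPIRIT versus usual care "will be evaluated and reported as an effect size estimate". Because the sample is small, the same section adds that "resampling methods will be used for all analyses and 95% bootstrap confidence intervals" will be used; the intervals are described as intervals for differences in outcome scores.

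Section 6.3 gives the allocation, "Dyads will be randomized with equal allocation (1:1) to SPIRIT or usual care", using "stratified (by race), permuted block randomization with block size 5". Section 8.1 lists the supplement's descriptors and possible covariates without saying which enter a model. For example, "Patients and surrogates will each complete a Sociodemographic Profile which includes demographic information and previous end-of-life decision-making experience", and dementia etiology, date of diagnosis and comorbid conditions are abstracted from the records. The Section 3 measurement table has congruence measured at baseline, and Section 4.2 gives control of confounding by race as the reason for stratifying.

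The only small-sample calculation, in Section 9.2, is that "a sample size of 30 will achieve 80% power to detect an effect size" of f² = 0.28, "attributable to the treatment group indicator using an F-test at a 5% significance level". That section also says that the pilot's effect sizes will be used to size later studies. Nowhere do the documents state the number of covariates, the estimator, the type of test for the group term, or what happens when a fit or a resample has no finite solution.

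**The concern.** A logistic regression with no qualifier is, by default, a maximum-likelihood fit. With 15 dyads per arm there are few dyads in the rarer outcome class, and each added covariate thins the data further. Maximum likelihood then tends to push a non-null log OR away from zero. In some data sets a combination of predictors separates congruent from incongruent dyads, and the OR estimate becomes infinite.

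Resampling does not cure either problem. It leaves the point estimate as it was, and resamples of 30 drawn with replacement are sparser than the data. The estimate affected is the pilot's effect size for its first hypothesis and is meant to feed the sample size of a larger trial. An exaggerated OR there leads to an underpowered successor.

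**Working it through.** **The plan's own figure.** Noncentral F with 1 numerator df and λ = f² × N = 0.28 × 30 = 8.4. Power is 0.799 with treatment as the only predictor (28 denominator df) and 0.793 with six predictors. The stated 80% is reproduced. It belongs to a linear-model F-test and says nothing about a binary outcome model; the documents give no figure for that.

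**Inputs.** From the documents: 30 dyads, 1:1, so 15 per arm. Assumed:
- Control congruence 48%. The figure is in the parent trial's power table, which does not label it a control rate; 30% and 70% were also run.
- True OR 2.0 (same table) and, as an illustrative upper value, 4.4. The latter is an earlier trial's 2-week result for the composite outcome, not congruence.
- The number, type and strength of covariates.

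**Information available.** At OR 2.0 the SPIRIT odds are 2.0 × 0.48/0.52 = 1.846, a rate of 0.649. Expected congruent dyads are 15 × 0.48 + 15 × 0.649 = 16.9, leaving 13.1 in the rarer class. Arm plus 2 covariates gives 13.1/3 = 4.4 such dyads per coefficient; arm plus 5 gives 13.1/6 = 2.2.

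**Simulated maximum likelihood.** Setting A adds baseline congruence, then race, then standard-normal covariates, all moderately prognostic (1,500 data sets per cell). Entries are exp(mean log OR) over finite fits.

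| Covariates | 0 | 1 | 2 | 3 | 5 |
|---|---|---|---|---|---|
| True OR 2.0 | 2.10 | 2.26 | 2.28 | 2.37 | 2.73 |
| True OR 4.4 | 4.85 | 4.98 | 5.30 | 6.50 | 8.75 |

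At true OR 1 there is no systematic shift.

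Setting B has baseline congruence 35% with OR 3 for the outcome, and other covariates unrelated to it. For true OR 2.0 it gives about 2.2, 2.5 and 2.8 with 2, 4 and 6 covariates. Across both settings, a true OR of 4.4 is estimated at about 5.3-5.6 with 2 covariates and 8.8-9.1 with 5-6.

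**No finite estimate in the trial's own data.** About 1-9% of data sets in the main runs of Setting A and 4-18% in Setting B (2-6 covariates). The worst variant of Setting A reached about 21%.

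**Bootstrap resamples that cannot be fitted (Setting A).**

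| Covariates | 1 | 2 | 3 | 5 |
|---|---|---|---|---|
| True OR 2.0 | about 7% | 19-20% | 19-20% | 34-38% |
| True OR 4.4 | 16-19% | 22-33% | 30-31% | 41-43% |

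Resampling within arm barely changes this. Taking both settings, the range with two or more covariates is about 20-58%. It is model-dependent and accurate only to several points.

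**Type I error at nominal 5% (3,000 data sets per cell).** Likelihood-ratio test: 3.8-5.1% with 0 covariates, 5.8-6.3% with 2, 7.8-8.2% with 3, 8.9-11% with 5. Wald test: 4.0-5.3% with 2-5.

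**Bias against sampling error.** With 2 covariates at OR 2.0 the bias is ln(2.28/2.0) = 0.13 on the log scale. The standard error is about 0.85, so a 95% interval spans a factor of exp(2 × 1.96 × 0.85) ≈ 28. With 5 covariates the bias is ln(2.73/2.0) = 0.31. At OR 4.4 with 5 covariates it is ln(8.75/4.4) = 0.69, below even the crude standard error √[1/(15 × 0.48 × 0.52) + 1/(15 × 0.802 × 0.198)] = 0.83.

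**Effect on a later trial.** Two proportions, 80% power, two-sided 5%, control 48%: a true OR of 2.0 needs 135 per arm. Planning on 2.28, 2.37 or 2.73 gives 97, 89 or 67 per arm, with actual power of about 66%, 62% or 50%.

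**Firth-penalised fits, Setting A, 1-5 covariates.** Estimates are 2.00-2.11 for true OR 2.0 and 4.3-4.9 for 4.4, and stay finite under separation. The penalised likelihood-ratio test rejects in 3.7-5.5% of null data sets with moderately prognostic covariates and 4.5-7.5% with non-prognostic ones (600 data sets each, 2-5 covariates).

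**The case against.** The strongest reply is that the size of the problem depends on a number the plan does not give. With 0-1 covariates at OR 2.0, Setting A shows bias of only 5-13%, a likelihood-ratio test near nominal size without covariates, and about 1-7% failed resamples. Section 8.1 lists what is collected, not what is modelled. This stands as a limit on size. But the stratification factor and the baseline value of the outcome are the natural first two covariates, and an open list lets the count grow.

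A second reply is that sampling noise dominates: crude power at 15 per arm is about 15% for OR 2.0 and 45% for OR 4.4, and Firth does not change that. This also stands. The bias is nevertheless systematic, in the harmful direction for planning, and cheap to remove.

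A reader might infer four stronger things that the documents do not support:
- **The group test is inflated.** No likelihood-ratio test is named. Wald is not inflated, and the promise of resampling leaves room for a permutation test.
- **The OR is always too large.** It is not shifted when the true OR is 1.
- **The plan commits to bootstrapping the OR.** The interval sentence concerns differences in scores; applying it to the OR rests on the words about all analyses.
- **The main trial is affected.** This is an additional model in a pilot, not the 400-dyad analysis.

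**Conclusion.** The concern holds in a limited form. Followed as written with two or more covariates, the plan yields a congruence OR that exaggerates a real effect: by roughly 10-15% with 2 covariates and 35-40% with 5-6 at a true OR of 2.0, and about twofold with 5-6 at 4.4. In a minority of data sets it yields no finite estimate. The promised resampling does not repair this and, if applied to the OR, would often fail.

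The sizes rest on the assumed 48% control rate, the assumed ORs and the assumed covariates. That the estimator is maximum likelihood is read from the plan's silence. Test inflation is conditional on choosing a likelihood-ratio test.

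**What to change.** In Section 9.4.2 (For Supplement Aims, Aim 1), replace the open-ended model with wording such as: *Post-intervention congruence will be analysed by Firth-penalised logistic regression with arm, baseline congruence and race stratum as the only terms. The adjusted odds ratio will be reported with a penalised profile-likelihood 95% interval. If a test of arm is wanted, a permutation p-value will be given. The difference in congruence proportions by arm will be reported alongside. Any bootstrap of the odds ratio will use the penalised fit; otherwise the odds ratio will not be bootstrapped.*

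The permutation p-value is preferable because the penalised likelihood-ratio test was not uniformly at 5% in the simulations. Exact or other penalised methods would also serve; what matters is a short named covariate list, a named small-sample estimator and a rule for fits that fail.

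The cost is a change of wording and standard software. The downsides are slight shrinkage of the OR towards 1 and adjustment for fewer covariates. The fix does not make the estimate precise, so the interval should travel with it into any later sample-size calculation.

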4 STUDY DESIGN**4.1 OVERALL DESIGN**

We will conduct a dialysis clinic-level cluster randomized trial with two groups, SPIRIT versus usual care followed by delayed SPIRIT. We will recruit 400 dyads of patients on chronic (“prevalent”) dialysis who are at high risk of death in the next year and their surrogate decision-makers (total 800 individuals) from 30 free-standing dialysis clinics in 4 states. The primary outcomes are patient and surrogate self-report preparedness for end-of-life decision making. The implementation evaluation data will be obtained throughout the study course. Upon patient death (anticipate 20% of patients; n = ~ 80), we will assess surrogates’ post-bereavement distress. Patient participation will end at 9 months (to allow for obtaining Medicare claims data during the study period) or death, whichever occurs first; surrogate participation will end at 9 months or at the completion of 3-month post-death follow-up. If patient is still living at 9 months, we will ask for an extension of follow up period to include 12 more months. Medicare claims data for end-of-life treatment intensity will be obtained quarterly. Clinics assigned to usual care will receive the delayed implementation, SPIRIT, in Year 4, Q1. This is a Phase III trial of an intervention that involves minimal risks and has proven to be efficacious, and thus no interim analysis is planned.

For Supplement Aims:

We will use a randomized controlled trial design with two groups: SPIRIT-dementia and usual care. From the pool of screened but excluded ESRD patients, we will recruit 30 dyads of patients with mild to moderate dementia and their surrogates. The groups will be stratified by race (white vs non-white). Patient and surrogate self-reported preparedness for end-of-life decision making will be measured at baseline and shortly after the intervention (by phone in the next 2-3 days) as done in the pilot test of SPIRIT-dementia. Additionally, we will review the patient's medical record to examine care decisions at 6 months or after the patient's death, whichever occurs first. In the case of patient death, we will also assess surrogates' post-bereavement outcomes (anxiety and depression symptoms) at 1 month after the patient's death. Based on previous research,¹³ we anticipate about 50% of the supplement sample will die within 12 months of enrollment. All data collection from study participants will be telephone-based.

Supplement cohort study:

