Virtually no trials are purely pragmatic or explanatory; based on the PRECIS Tool and key characteristics of pragmatic trials,^{66,67} the proposed study is more pragmatic than explanatory in the pragmatic-explanatory continuum because it will include diverse patient populations, multiple heterogeneous settings, few inclusion and exclusion criteria, and the comparison condition is a real-world alternative (i.e., usual care), not a placebo. Further, the study is built around normal dialysis care operations as much as possible with flexible study protocols that minimize intrusion in daily work flow at the dialysis facilities. Of direct relevance to dialysis care, the intervention will be implemented by dialysis care providers, such as nurses and social workers.

For Supplement Aims:

As in our previous studies of SPIRIT, we chose individual randomization because intervention spillover to the control condition is very unlikely. The intervention will be delivered by a trained interventionist, not a care provider, in a private room at the clinic, or virtually due to the COVID-19 pandemic, and thus it is nearly impossible for care providers to obtain the knowledge and skill related to SPIRIT to change their ACP practice. We chose race (white vs non-white) as a stratification factor to ensure equal allocation of race to each condition to control for race as a confounding variable.⁴⁹

The follow-up time point (2-3 days post intervention) is to evaluate the impact of SPIRIT on preparedness outcomes while minimizing the potential influence of the patient's impaired ability to recall what was discussed during the SPIRIT session. We considered measuring the outcomes immediately following the intervention, but this would increase subject burden as SPIRIT sessions tend to last longer with PWDs than those without cognitive impairment. The time point for care decision reviews (6 months post intervention) was chosen to help maximize the number of patients whose conditions progress within the study period so that we can explore the impact of SPIRIT-dementia on care decisions. As in earlier SPIRIT trials and the parent study with ESRD patients and the parallel study with dementia patients, we will use telephone-based data collection to reduce participants' travel burden.

Supplement cohort study:

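### Dementia pilot: bereavement HADS is compared by an unadjusted t-test in about 15 surrogates although baseline HADS is collected, and no baseline-adjusted model is written for the other scores

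*Combined protocol and SAP*

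**What the plan says.** Section 4.1 sets the size of the pilot: "we will recruit 30 dyads of patients with mild to moderate dementia and their surrogates". Section 6.3 specifies "stratified (by race), permuted block randomization" and adds "Dyads will be randomized with equal allocation (1:1) to SPIRIT or usual care". Section 4.2 gives the reason for stratifying: "to ensure equal allocation of race to each condition to control for race as a confounding variable".

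Section 8.1 (Supplement Aims) has the preparedness measures taken at baseline and 2-3 days after the intervention. The surrogate's HADS is an instrument "which will be completed at baseline and 1 month post patient death".

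The analysis is in section 9.4.2 (Supplement Aims):

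- **HADS:** "Differences in the HADS subscale scores between the intervention and control groups will be assed using t-tests". The expected number is 15, from a 50% death rate among 30. The standardised difference is the effect-size estimate.
- **Congruence:** McNemar's test, plus a logistic model that adjusts for covariates it does not list.
- **DCS and DMC:** both are hypotheses in section 9.1, but no between-group model is written for either.
- **All analyses:** resampling methods, with 95% bootstrap intervals for the differences.

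Section 9.2 says that the pilot's effect sizes will feed sample-size calculations for later, larger studies.

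**The concern.** With 7 surrogates in one arm and 8 in the other, the arms can differ noticeably in baseline HADS by chance. An unadjusted comparison carries that difference, in proportion to r, into the estimate. A bootstrap interval around the same unadjusted difference shows its variability but does not remove the imbalance.

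The plan also departs from the team's practice elsewhere in the same document. The earlier efficacy trial's bereavement results in 45 surrogates (section 2.2) were adjusted for baseline values. The COVID-19 cohort supplement (section 9.4.2, its Aim 3) uses analysis of covariance on the preceding value of each outcome. No reason is given for treating the pilot differently.

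At stake is the quality of an effect-size estimate that is already imprecise. For DCS, DMC and congruence, leaving the model or its covariates open also means that choices made after seeing the data could move the reported effect size.

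**Working it through.** **1. The plan's own figure.** Section 9.2 claims 80% power for Cohen's f² = 0.28 with N = 30, "using an F-test at a 5% significance level". Noncentrality = 0.28 × 30 = 8.4. With 1 and 28 degrees of freedom, power is 79.9%, so the figure reproduces. It corresponds to a two-sided t-test with 15 per arm at d = 2√0.28 = 1.06. The other stated figure, n = 15, is 0.50 × 30.

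**2. Precision of the planned HADS test.** Assume a 7 vs 8 split.

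- 95% half-width = t(0.975, 13) × √(1/7 + 1/8) = 2.160 × 0.518 = 1.12 SD.
- Difference detectable with 80% power: 1.57 SD.
- Power at a 1-SD difference: 43%.

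**3. Chance imbalance.** The difference in mean baseline HADS also has a standard deviation of 0.518 SD. The arms then differ by more than 0.5 SD with probability P(|Z| > 0.5/0.518), about one in three. If r = 0.5 (assumed), an imbalance of 0.5 SD shifts the t-test estimate by 0.5 × 0.5 = 0.25 SD.

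**4. Effect of baseline adjustment on interval width.** With k covariates,

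width ratio = √[(1 - r²)(N - 3)/(N - 3 - k)] × t(0.975, N - 2 - k)/t(0.975, N - 2).

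The factor (N - 3)/(N - 3 - k) is the cost of chance covariate imbalance. Leaving it out would overstate the gain.

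- N = 15, k = 1: √(12/11) × 2.179/2.160 = 1.053, then × √(1 - r²).
- N = 30, k = 1: √(27/26) × 2.052/2.048 = 1.021, then × √(1 - r²).

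| r (assumed) | n = 15, baseline only | n = 30, baseline only |
|---|---|---|
| 0 | +5% | +2% |
| 0.3 | 0% | -3% |
| 0.5 | -9% | -12% |
| 0.7 | -25% | -27% |
| Break-even r | 0.31 | 0.20 |

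For HADS at n = 15, power at a 1-SD difference moves from 43% to 40%, 50% and 66% at r = 0, 0.5 and 0.7. A simulation (6,000 runs per value of r) agrees: 40%, 51% and 67%. At n = 30 and r = 0.5, power at d = 1.06 rises from 80% to 89%.

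**5. Adding race as well.** Assume race is unrelated to the outcome. At n = 15 with k = 2, the factor is √(12/10) × 2.201/2.160 = 1.116. The half-widths are 1.19, 1.08 and 0.89 SD at r = 0.3, 0.5 and 0.7, against 1.12 for the t-test, and break-even rises to about 0.44. At n = 30 it is about 0.28, and power at d = 1.06 with r = 0.5 is 87%.

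**The case against.** The strongest reply is that a t-test in a randomised comparison is valid, if imprecise, and that nothing confirmatory depends on it. That stands, and it sets the severity.

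The correlation may also be low. Baseline HADS is taken before bereavement, possibly many months before. Section 8.1 reports that distress in the efficacy trial rose sharply 2 weeks after the death and had stabilised by 3 months, while the pilot measures at 1 month. A correlation above 0.31 is plausible but cannot be presumed. This stands too, so the gain is conditional.

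A reader might infer more than the documents support, in four ways:

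- **That race is ignored throughout.** The logistic model does adjust for covariates. Section 8.1 (Supplement Aims) lists demographic information under Descriptors and Potential Covariates, so race can enter. The gap is pre-specification. The baseline outcome scores are not on that list. McNemar's test seems to use baseline congruence, but it does not compare the arms.
- **That DCS and DMC will be analysed unadjusted.** No between-group model is written at all. The F-test for the group indicator in section 9.2 is compatible with a model that has covariates.
- **That adjustment is a free gain.** Step 5 shows that baseline plus race widens the HADS interval at r = 0.3. Section 2.2 expects a largely African American sample, so the white stratum among 15 bereaved dyads could be nearly empty. For the same reason, bootstrapping within arm-by-race cells should not be asked for.
- **That the precision argument covers congruence.** In a logistic model, covariate adjustment generally does not shrink the standard error of the log odds ratio. There the case is pre-specification and baseline imbalance.

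**Conclusion.** The point holds as a minor one. The plan states an unadjusted t-test for HADS, although the baseline value of the same scale is collected and the team adjusted for it in its own earlier trial. It leaves the DCS and DMC models unwritten and the logistic covariates unnamed.

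If r is near 0.5, baseline adjustment narrows the HADS interval by about 9% and the 30-dyad intervals by about 12%. If r is near zero, it widens them by about 5% and 2%. These figures rest on an assumed r, a 7 vs 8 split among 15 bereaved surrogates (15 per arm for the full sample), and a linear relation with common variance.

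The case for carrying race into the 30-dyad analyses is consistency with the stratified design, since an unadjusted test tends to be conservative when the stratum is prognostic. A gain in precision from race is not assured. In the HADS subset, which is defined by deaths after randomisation, the stratification does not guarantee racial balance.

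**What to change.** In section 9.4.2 (Supplement Aims):

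1. Analyse HADS anxiety and depression at 1 month after death with a linear model on arm and the baseline value of the same subscale. Keep the unadjusted t-test as a sensitivity analysis.
2. Analyse DCS and DMC at 2-3 days with a linear model on arm and the baseline value of the same score.
3. List the covariates of the logistic model, and include baseline congruence among them.
4. Include race, the stratification factor, in the analyses of all 30 dyads unless a stratum is too sparse. State in advance what counts as too sparse.
5. Apply the planned bootstrap to the adjusted differences, without requiring resampling within arm-by-race cells.

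This is a cheap improvement. Every variable is already collected, so only the wording of the plan changes. The price is one degree of freedom for HADS and one or two in the 30-dyad analyses, with a slightly wider interval if baseline turns out to be weakly prognostic.
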